and 3) is conducive to examining sleep.

Recent advances in electroencephalographic recording techniques have produced new ways to probe the process and function of sleep. Through the use of high-density EEG (hdEEG, 256 channels), we are able to approach the spatial resolution of other brain imaging modalities while affording the millisecond temporal resolution of EEG and providing a direct measure of the underlying brain activity, unlike the indirect and/or secondary biophysical signals of brain hemodynamics/metabolism obtained with PET or fMRI that are suboptimal for exploring the short-lived spatio-temporal dynamics of many brain processes. While most EEG analysis is

Most likely these conflicting results are related to limited time imaging windows (both during sleep onset, but SPECT integrating only over several minutes). What is needed is to explore the role of hyperarousal in insomnia as an imaging tool that is able to 1) resolve temporally whether hyperarousal is constant, fluctuates based on the ongoing pattern of EEG, or is a specific, abnormal reaction to incoming stimuli; 2) resolve spatially the difference between global and regional cortical arousal; and 3) is conducive to examining sleep.

performed using scalp voltages, the use of hdEEG provides sufficient data to accurately model the cortical sources of scalp electrical activity. Our group at UW has developed hdEEG in sleep as a neuroimaging tool and demonstrated its utility for studying the role of sleep in normal brain function. For example, we have shown that both slow waves and spindles, characteristic sleep EEG waveforms, are useful measures of localized brain activity. HdEEG has revealed that sleep is more intense (more slow wave activity, EEG power between 0.5 – 4 Hz) in the cortical regions that learn the most during waking, thus demonstrating that not only do slow waves reflect sleep intensity, but they also reflect the underlying the cellular need for sleep in a regionally specific manner (Huber et al 2007, Huber et al 2006, Huber et al 2004, Huber et al 2008, Matta et al 2010, Sarasso et al 2010). Additionally, sleep slow waves have been shown to travel across the cortical mantle from distinct origins (Massimini et al 2004). Notably, the cortical hot spots for slow wave origination and propagation include the insula and the anterior cingulate, PET-identified regions of hyperactivation in insomnia (Murphy et al 2009)(Figure 1).

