N2 (%)	64.37 (7.43)		60.24 (9.19)		59.67 (9.20)		2,24	0.79	.465	—	—	—
N3 (%)	8.63 (6.71)		10.64 (12.15)		14.77 (9.66)		2,24	0.92	.411	—	—	—
REM (%)	14.44 (5.71)		19.76 (6.64)		18.32 (4.85)		2,24	2.03	.153	—	—	—
REML (min)	107.72 (30.43)		97.44 (46.66)		101.72 (18.92)		2,24	0.21	.814	—	—	—

Table 1: Comparison between insomnia (PI) and good sleep control (GSC) subjects on sleep and demographic measures. HRSD = Hamilton Depression Rating. ISI = insomnia severity index. ESS = Epworth Sleepiness Scale. TST = Total sleep time. WASO = Wake after sleep onset. AI = Arousal index. SE = Sleep efficiency. SOL = Sleep onset latency. REML = REM latency. % expressed relative to TST. Modified from Goldstein APSS 2013.

[figure not shown]

Figure 2: Increased cortical alpha during deeper sleep in insomnia patients. Cortical flat map showing areas with significantly increased alpha (8 – 12 Hz) activity when comparing insomnia patients to good sleeping controls (SnPM cluster test, t-threshold based on $\alpha < 0.05$, 1000 permutations, 9 subjects per group). 5 minutes of NREM sleep selected from the middle of the 1st NREM episode cycle (including N3 in all but 1 insomnia patient) was band-pass filtered prior to source localization (Geosource, 4-shell head model, minimum norm solution with sLORETA constraint, tikhonov regularization -1).

order to increase our localization power, to see whether this increase persists throughout the night during normal sleep, or is specific to stage N3, and to determine if it is particularly associated with sleep onset and/or sleep maintenance difficulties; we will also examine how this finding relates to the process of falling into and arousing from sleep.

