2.3 Defining abnormal activity during sleep transitions in insomnia with hdEEG

[figure not shown]

Figure 3: The relative involvement of sensory brain regions in slow waves progressively increase during the descent into sleep.
 Cortical flat map shows significantly different slow wave involvement (based on the Wilcoxon Signed rank test, 6 subjects) when comparing the early (2-3, red) to late (8-9, blue) falling asleep periods. To compare results obtained in different epochs and subjects, relative involvement is computed as the ratio between the value in each voxel and the value resulting from the average of all brain voxels. Modified from Siclari et al. *in preparation*.

subjects to systematically wake them up throughout the night) in a group of normal subjects to describe how different waveforms contribute to falling asleep in a regionally specific manner by examining hdEEG during equally distributed time periods between the end of posterior alpha (10-20 channel Oz) and the first slow wave burst (2 consecutive slow waves without an arousal (Siclari et al. *in preparation*). In good sleeping controls, slow waves followed two spatially and temporally distinct processes during the transition from wakefulness to sleep. The early process was characterized by isolated, large amplitude slow waves that involved mainly the frontal regions and was associated with high gamma power. The late process was marked by numerous smaller slow waves that tended to originate more diffusely over the cortex, and to involve also the temporal, lateral parietal and occipital brain regions. The falling asleep process is thus characterized by a transition from predominantly local to increasingly global sleep patterns. This process may be disrupted in insomnia, particularly given the similarities between areas from which slow waves involved only later in the falling asleep process originate and areas exhibiting alpha activity during deep NREM sleep in insomnia patients.

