2. Define cortical source abnormalities in the processes of falling asleep and arousing from sleep in insomnia patients with and without depression compared to healthy sleeping controls.

3.2 Secondary Objectives:

1. Correlate abnormalities in sleep EEG patterns with specific insomnia symptoms, including sleep onset difficulties, sleep maintenance problems, nonrestorative sleep and daytime dysfunction.

Insomnia and Sleep Patterns Study

2. Define abnormalities in overnight changes in waking EEG activity in insomnia patients with and without depression compared to healthy sleeping controls.
3. Explore whether abnormalities in sleep and waking EEG activity in insomnia patients, with and without depression, normalize following treatment with a sleep medication.

3.3 Clinical Hypotheses:

1. Insomnia patients will show increased regional EEG alpha activity in sensory cortical areas particularly during sleep.
2. Insomnia patients will show abnormalities in the process of sleep initiation, including regional sources of high frequency EEG activity that will interfere with the normal progression of the sleep process.
3. Insomnia patients will show abnormalities in the regional patterns of cortical arousal responses to external stimuli during sleep, particularly in the sensory cortical areas exhibiting increased alpha activity.
4. Abnormalities in sleep EEG patterns may be correlated with specific insomnia symptoms, particularly difficulty with sleep initiation or maintenance.
5. Waking EEG in insomnia patients will not show overnight recovery compared to controls, which will be correlated with specific EEG abnormalities during sleep, such as elevations in higher frequency activity.
6. Explore whether insomnia patients with and without depression differ in abnormalities in sleep EEG patterns.

4. Research Design and Methods

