4.4.2 Proposed Data Analytic Strategy

[name] [name] (PI), [name], and [name] will be responsible for performing and overseeing data collection and analysis. Statistical analysis will be planned and executed in conjunction with UW BARD (<https://ictr.wisc.edu/Biostatistics>). Although our preliminary work has allowed us to identify several primary objectives, described below, with clearly identified primary outcome measures and *a priori* analysis plans, the protocol is also largely designed to be exploratory in nature. Therefore, it is likely that several promising analysis paths will emerge once the data have been collected that cannot be formally identified in advance, but that are in keeping with the primary and secondary objectives of the study. Such additional exploratory analyses naturally raise the issue of multiple comparisons. Our laboratory has been a leader in designing and implementing the use of hdEEG in sleep, particularly in clinical populations, and has been successful in funding and publishing this type of exploratory research. Where appropriate, established procedures will be used to evaluate a family of related questions (e.g., ANOVA for comparison between groups across frequency bands) with reasonably chosen post-hoc corrections for multiple comparisons (e.g., Bonferroni). However, in all cases these procedures will be adapted to account for the most pervasive multiple comparison problem in hdEEG and other neuroimaging (independent tests between hundreds of electrodes or thousands of potential cortical sources) using statistical nonparametric mapping techniques (SnPM) as described below.

Normal hdEEG sleep imaging (Primary Objective 1)

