order of minutes instead of hours. Preliminary results suggest that tonic alpha power during N3 sleep may distinguish between these groups, but it is also conceivable that events like slow waves or spindles may provide additional distinguishing information, and windows around these events may be relevant. The **outcome measure** addressing **this first primary study objective** will be the cortical localization maps of band-pass filtered EEG data in the frequency range of interest (identified by the scalp-level analysis from the initial steps, e.g. alpha) using a distributed inverse solution (i.e. LORETA, for details of the methods involved see (Murphy et al 2011)). All group comparisons of distributed source localization maps will be analyzed using statistical nonparametric mapping (SnPM)(Nichols & Holmes 2002) which is ideally suited to address the multiple comparison issues inherent to neuroimaging and which does not make unwarranted assumptions about data distribution. This method has been successfully applied in a number of hdEEG studies in our laboratory (Ferrarelli et al 2007, Huber et al 2006, Huber et al 2004), and compares favorably with Statistical Parametric Mapping for analyses having low degrees of freedom.

Falling asleep imaging (Primary Objective 2a)

During both the baseline and serial awakening sleep nights, the descent into (or back into) sleep will be analyzed by dividing the interval between the last appearance of occipital alpha and the first instance of a burst of slow waves (more than 2 slow waves consecutively without an arousal) into 10 equally spaced temporal bins prior to cortical source estimation. Distributed source localization maps for individual frequency ranges will then be average within subject and then within group prior to statistical analysis.

Sleep arousal imaging (Primary Objective 2b)

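### The planned source-map comparison cannot separate a sensory-cortex alpha increase from a global one, so a global increase could be read as regional

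*Combined protocol and SAP*

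**What the plan says.** Section 3.3, Hypothesis 1, is a statement about location: "Insomnia patients will show increased regional EEG alpha activity in sensory cortical areas particularly during sleep". Section 2.2 gives the reason for using high-density EEG, namely a tool able to "resolve spatially the difference between global and regional cortical arousal".

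Section 4.4.2 (Normal hdEEG sleep imaging) sets out the analysis for Primary Objective 1. The outcome "will be the cortical localization maps of band-pass filtered EEG data in the frequency range of interest", obtained "using a distributed inverse solution (i.e. LORETA, for details of the methods involved see" a cited paper. The group test is SnPM: "All group comparisons of distributed source localization maps will be analyzed using statistical nonparametric mapping (SnPM". The opening of 4.4.2 presents SnPM as the answer to multiplicity, that is to "independent tests between hundreds of electrodes or thousands of potential cortical sources".

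Section 4.4.2 gives no scaling of the maps to a whole-brain value, no group-by-region contrast and no predefined sensory region for testing Hypothesis 1. A region-of-interest approach appears only for correlations with behavioural variables and, in the exploratory Cox regression, for regions taken from the baseline analysis. Whole-brain scaling is described once, in the Figure 3 caption (section 2.3), for slow waves during sleep onset: "relative involvement is computed as the ratio between the value in each voxel and the value resulting from the average of all brain voxels".

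**The concern.** A between-group map test asks, at each source or cluster, whether patients and controls differ. Hypothesis 1 asks whether sensory sources differ more than the rest of the cortex. A significant area beside a non-significant area does not answer the second question, because the difference between the two areas has not been tested.

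A global component is plausible. Section 2.2 reports that beta and gamma were raised globally in the pilot, and describes the earlier PET effect as global although highest in several regions. If alpha also rose everywhere, noise and thresholding could leave a patch that is taken as evidence that sensory cortex in particular stays active. That reading would carry forward: Hypothesis 3 builds on the sensory areas with raised alpha, and the Cox regression uses regions found at baseline.

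**Working it through.** **1. The plan's own figure.** Section 4.4.1 gives d = 1.15, 20 per group, two-tailed alpha 0.05, power about 94%. For a two-sample t test the noncentrality is d × √(n/2) = 1.15 × √10 = 3.64 on 38 degrees of freedom, and power is 94.3%. With 10 per group it is 68.2%, against the stated 68%. Both reproduce. They concern the cluster-average difference between groups, not regional specificity.

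**2. What each test examines.** Let δ(v) be the group difference in log alpha at source v. SnPM tests δ(v) = 0. Hypothesis 1 needs Δ = (mean of δ over sensory sources) − (mean of δ over the rest) > 0. If δ(v) = δ everywhere, the first null is false at every source while Δ = δ − δ = 0. Rejecting the first therefore says nothing about Δ. The pilot used a "SnPM cluster test, t-threshold based on" a nominal level (Figure 2 caption); cluster inference does not change this.

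**3. How often a global effect gives a partial map.** The documents give n = 20 per group and d = 1.15. Assumed: the same d at every source, spatial smoothness, 30–60% of between-person variance shared by all sources, d = 0.6 and 0.8 as smaller effects, and coverage below 75% of the map as the mark of a partial map. The cells show the share of all simulated studies with a significant but partial map.

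| Uniform d | Cluster test | Single-source maximum statistic |
|---|---|---|
| 1.15 | 4–13% | 58–88% |
| 0.8 | 35–43% | 77–91% |
| 0.6 | 41–62% | not run |

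The right-hand column is (share positive) × (share of positives below 75%): at d = 1.15, 0.98 × 0.59 = 0.58 and 1.00 × 0.88 = 0.88; at d = 0.8, 0.80 × 0.96 = 0.77 and 0.91 × 0.995 = 0.91. A further cluster-test run on a 20 × 20 smooth field gave 6–6.5% at d = 1.15 and 36–52% at d = 0.8.

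**4. A different geometry.** With 200 sources on a ring, shared correlation 0.3–0.9, and any map short of complete counted as partial, the cluster test gave partial maps in 8–50% at d = 1.15, 29–86% at d = 0.8 and 32–70% at d = 0.6. At d = 1.15 it marked the whole map in 50–88%. The criterion is looser than in step 3, so the ranges are wider; the direction is the same.

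**5. After removing each person's map mean.** The same purely global effect gave positives of any extent in roughly 3–10% in the setting of step 3 (cluster test), and in 2–6% (cluster) or about 5–6% (maximum statistic) on the ring at d = 1.15. The Monte Carlo standard error for 5% with the 200 data sets used on the ring is √(0.05 × 0.95 / 200) = 1.5 points, so the ring results are compatible with 5%.

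**The case against.** A reader might infer that the plan tests un-normalised maps and that a global increase would be reported as regional. The documents do not support either step. Section 4.4.2 is silent on scaling and leaves map construction to a cited paper, and Figure 3 shows that this group does scale to the whole-brain mean in other work. In section 2.2 the team called the pilot beta and gamma increases global, so it does report global results as global.

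The size can also be overstated. The high percentages come from a single-source threshold, whereas the pilot used a cluster test. At d = 1.15, the only effect size given, a uniform effect usually fills most of the map under a cluster test. A patch must also fall in the right place: with an assumed sensory region of 24% of the map, significant coverage there was at least twice that elsewhere in only 0–2% (cluster) or 3–13% (maximum statistic) of purely global data sets. Finally, Primary Objective 1 is worded as examining differences, which SnPM does, and 4.4.2 describes the protocol as largely exploratory.

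These points lower the severity. They do not close the gap. The document states scaling where it was used (a ratio to waking baseline in Figure 1, to the whole-brain average in Figure 3) and mentions none in the detailed Figure 2 caption or in 4.4.2. Section 4.4.2 also claims identified outcome measures and a priori analyses for the primary objectives, and no test of Δ is among them. Since 1.15 is an average over a cluster already found significant, smaller effects, where partial maps are more common, cannot be set aside.

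**Conclusion.** The point holds as a gap in the stated analysis. Nothing in 4.4.2 separates a regional sensory increase from a global one, so a significant SnPM area would not by itself support Hypothesis 1, and a global increase could be read as regional. That conclusion is logical and rests on no simulation.

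The frequency does rest on assumptions about smoothness, shared variance and a uniform effect. With 20 per group, a cluster test and 30–60% shared variance, partial maps under a purely global effect occur in roughly 4–13% of studies at d = 1.15 and 35–62% at d = 0.6–0.8, and more often with a single-source threshold. The documents do not show that the pilot alpha finding was global, and the stated 94% power is not in error. This is a cheap improvement that should be made, not a defect that must be cured before the study can be used.

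**What to change.** In 4.4.2:

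- State how the source maps are scaled before group comparison. If the cited method already scales them, one sentence settles that part.
- Keep SnPM on absolute maps for the question of whether there is a difference.
- Define the sensory region before group maps are seen, and prespecify one two-sided group contrast of log alpha, sensory region minus rest of cortex, naming the groups and sleep window. Make it the sole test that licenses the words regional and sensory for Hypothesis 1, and only when it shows a relative increase.
- Report SnPM on whole-brain-normalised maps as supportive only. It can be positive outside sensory cortex or through a relative decrease. Accepting either it or the contrast, uncorrected, gave 9.5–16.5% positives in one simulation of a purely global effect.
- Otherwise describe any increase as global or not localised.

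The cost is a few sentences and a little extra analysis of data already collected. The real downside is that power for the relative effect is unknown: the documents give no effect size for it, and the 94% concerns the cluster average. A global or weakly regional effect could then no longer be called sensory.

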may repeat the waking EEG, evoked potential recordings, arousal measures, and attention tasks. They will also complete some questionnaires prior to bedtime (i.e., VAS and STAI). Additional PSG channels (including EOG, EMG, EKG, and optional PSG sensors if warranted) will be applied prior to lights out to assist in accurate sleep staging. All participants will then complete the serial awakening night in which participants are periodically probed with auditory stimuli during the night. After the onset of sleep, participants will be awakened repeatedly using 10 sec tones starting at 40dB and increasing by 5 dB every 30 sec until a full awakening is achieved. This procedure has been used effectively to estimate the effects that background alpha and sleep spindle activity have on sleep stability (Dang-Vu et al 2010, McKinney et al 2011). After indicating that they have heard the tone, subjects will confirm that they are awake by answering two questions “What was the last thing going through your mind after hearing the sound” and “were you awake or asleep”. Participants will then be encouraged to fall back asleep. We will aim to evoke at least 1-2 awakenings in each stage (N1, N2, N3, REM) for the first 3 sleep cycles so as to have a minimum of 12 total awakenings. The timing of these awakenings will be approximated based on the sleep architecture of the baseline night. Sleep recordings will end when the participant awakens in the morning, or if they cannot return to sleep during the night. No awakenings will be attempted after the subject’s normal waking time and they will be allowed to sleep *ad libitum* after this time if they wish. Participants will also complete some questionnaire measures upon awakening, including measures of arousal and mood (e.g., GCTI, PSAS, VAS, STAI, Post-Sleep Questionnaire), as well as waking EEG, evoked potential recordings, and the brief attention tasks if time permits. As before, participants will be under constant staff supervision during the recording. If participants are unable to sleep longer but do not feel rested, we will provide transportation back home.

Follow-up hdEEG Sleep Recording (Visit 4)

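### The Objective 2a falling-asleep window closes only at a slow-wave burst, so a return to REM after an awakening puts established REM sleep into a primary-outcome map

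*Combined protocol and SAP*

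**What the plan says.** Section 4.4.2, Falling asleep imaging (Primary Objective 2a), sets one rule for all descents: "During both the baseline and serial awakening sleep nights, the descent into (or back into) sleep will be analyzed". The window is "the interval between the last appearance of occipital alpha and the first instance of a burst of slow waves". The burst definition and the binning follow: "more than 2 slow waves consecutively without an arousal) into 10 equally spaced temporal bins prior to cortical source estimation". There is no maximum length and no other closing event. The maps are then pooled: "Distributed source localization maps for individual frequency ranges will then be average within subject and then within group prior to statistical analysis".

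The next part of 4.4.2 (Sleep arousal imaging) makes cortical maps over predefined windows the outcome measures of the second primary objective.

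Section 4.2.2, Serial Awakening hdEEG Sleep Recording (Visit 3), describes where the returns to sleep come from: "We will aim to evoke at least 1-2 awakenings in each stage (N1, N2, N3, REM) for the first 3 sleep cycles". The stated floor for the night is 12. After each awakening the participant is encouraged to go back to sleep.

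Section 2.3 describes the process that the window was built to capture: "The falling asleep process is thus characterized by a transition from predominantly local to increasingly global sleep patterns". That account concerns slow waves, first isolated and frontal, later numerous and widespread.

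**The concern.** A slow-wave burst is a sensible end marker for a passage from wake into NREM. It is not one for a passage from wake into REM. A participant who is woken from REM and goes back into REM, directly or after a little N1, may produce no burst until the next NREM period. Read literally, the window then holds three things: the short descent, the rest of the REM episode, and the later entry into NREM. All of it is cut into 10 bins and treated as falling asleep. A spontaneous awakening from REM on either night can do the same.

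Nothing in 4.2.2 or 4.4.2 ends the window at scored REM, caps its length, or separates descents by the stage before or after the awakening. Stages are scored in 30-second epochs, but the scores are not used to define or filter the 2a window. The independent component step for REM removes artifacts and keeps the REM data.

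Hypothesis 2 in section 3.3 is about regional high-frequency activity during sleep initiation. Bins that hold established REM do not measure initiation, yet they enter the average that is meant to test it.

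**Working it through.** **Inputs from the documents.** At least 1 awakening per stage, 4 stages, 3 cycles, minimum 12 awakenings (4.2.2). Ten equal bins per descent, on two nights (4.4.2).

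**Inputs not in the documents, assumed here.** Descent D = 2 min; remaining REM R = 5, 10 or 20 min; time from the end of REM to the burst B = 2 min; probability p = 0.2, 0.5 or 0.8 that an awakening from REM is followed by a return to REM.

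**1. The plan's own count.** 1 × 4 × 3 = 12, which reproduces the stated minimum. From REM: 1 × 3 = 3, or 3/12 = 25% of probes.

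**2. Content of one affected window.** Length = D + R + B, bin width = length/10, REM share = R/length.

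| R (min) | Length (min) | Bin width (min) | REM share | Bins more than half REM |
|---|---|---|---|---|
| 5 | 9 | 0.9 | 5/9 = 56% | 6 of 10 |
| 10 | 14 | 1.4 | 10/14 = 71% | 8 of 10 |
| 20 | 24 | 2.4 | 20/24 = 83% | 8 of 10 |

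A second layout leaves out the final NREM segment (B = 0) and varies D from 1 to 5 min with the same R. REM is then between 5/10 = 50% and 20/21 = 95% of the window, and 5 to 9 of the 10 bins are wholly REM. With R = 0, a return through NREM, no bin is affected.

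**3. Share of descents affected.** The 12 probed returns plus one initial onset on each of two nights give 14 planned descents. Share = 3p/14:
- p = 0.2: 0.6/14 = 4%
- p = 0.5: 1.5/14 = 11%
- p = 0.8: 2.4/14 = 17%

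Against the 12 probed returns alone the shares are 5%, 12.5% and 20%. With k further spontaneous returns through NREM the share is 3p/(14 + k), so it falls. Spontaneous awakenings from REM that lead back to REM would add to the numerator. The documents give neither count.

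**4. REM in the pooled data.** If each descent counts equally and R = 10 min, the overall REM fraction is (3p/14) × (10/14), about 3%, 8% or 12%. REM is concentrated in the middle bins, where its share of descents can reach the 4% to 17% of step 3.

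**The case against.** The strongest reply has five parts.

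- **The start marker.** The window begins at the last occipital alpha. Alpha that reappears during REM, or at a brief arousal, would move the start later and shorten the window. This stands against the exact lengths above. It does not rescue the rule: a window that starts inside REM is still not a descent from wake. If the participant truly wakes again after REM and then enters NREM, that later interval is a proper descent and is not in question.
- **The probing schedule.** A further probe before any burst leaves the interval with no end point, so it may yield no window. That makes the 20-minute case less likely on the probed night. The REM awakenings are also a target, not a guarantee.
- **Common sense.** An analyst might simply not call a REM-filled interval a descent. But the plan does not record that choice, so it could be made after the maps are seen.
- **The exploratory character of the protocol.** 4.4.2 does say that much of the work is exploratory. It also presents the windows for this primary objective as predefined.
- **Selection by the remedy.** Excluding by what follows the awakening can remove different numbers of descents in different groups. This stands, and is why the counts must be reported.

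A reader might infer a bias between groups from the pilot table in section 2.2, where REM was 14.44% of sleep in insomnia and 18.32% in controls. The documents do not support that step. The three-group test for that row was F(2,24) = 2.03, p = .153, with 9 per group. The measure is also a share of total sleep time, not a rate of returning to REM after an awakening.

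**Conclusion.** The point holds in a conditional form. When a participant re-enters REM before a slow-wave burst, the stated rule places established REM in the falling-asleep bins of a primary-outcome map. That follows from the text, and it is a rule that misfires rather than a detail left open.

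Its size is not known from the documents. Under the assumed durations, REM takes about 56% to 83% of an affected window. Under the assumed return rates, about 4% to 17% of 14 planned descents are affected, and a smaller share once spontaneous returns through NREM are added. First sleep onsets that pass into NREM are untouched.

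The consequence that can be claimed is a mixture of two states in the averaged bins. A difference between groups would need different return-to-REM rates, which nothing in the documents shows. A reader might also infer that REM dominates the Objective 2a data because affected windows are long. That would require weighting by time, whereas cutting each interval into the same number of bins and averaging within subject reads more naturally as equal weight per descent.

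**What to change.** In 4.4.2, Primary Objective 2a:

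1. Limit the main maps to descents into NREM. Exclude any interval with an epoch scored REM between the awakening (or lights out) and the first slow-wave burst. Anchoring at the awakening keeps the filter independent of how the last occipital alpha is read.
2. Analyse returns to REM separately as exploratory, with the window ending at the first REM epoch.
3. Report the number of excluded descents by group.

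The cost is a few lines of text and a filter on stage scores that the plan already produces. At the 12-probe minimum, up to about 3 of 12 probed descents per person leave the main average. Those descents do not measure entry into NREM. Ending every window at REM onset, or stratifying by the stage entered, would also work; what matters is that the choice is written down before the maps are examined.
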